## 2.3 Endpoints

### 2.3.1 Primary Endpoint

Proportion of subjects who have died or progressed to RF as defined by progressing to the need for high-flow nasal cannula O2 delivery, noninvasive positive pressure ventilation, invasive mechanical ventilation, or extracorporeal membrane oxygenation (ECMO) therapy at Day 28.

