**Table 2: World Health Organization Ordinal Scale for COVID-19**

Patient State	Description	Score
Uninfected	No clinical or virological evidence of infection	0
Ambulatory	No limitation of activities	1
	Limitation of activities	2
Hospitalized, Mild Disease	Hospitalized, no oxygen therapy	3
	Oxygen by mask or nasal prongs	4
Hospitalized, Severe Disease	Noninvasive ventilation or high-flow oxygen	5
	Intubation and mechanical ventilation	6
	Ventilation + additional organ support – pressors, RRT, ECMO	7
Dead	Death	8

Abbreviations: ECMO = extracorporeal membrane oxygenation; RRT = renal replacement therapy

6. Proportion of patients who develop critical COVID-19 illness as defined by at least one of the following:
  - A. RF defined based on resource utilization requiring at least one of the following: Endotracheal intubation and mechanical ventilation, oxygen delivered by high-flow nasal cannula (heated, humidified, oxygen delivered via reinforced nasal cannula at flow rates > 20 L/min with fraction of delivered oxygen  $\geq 0.5$ ), noninvasive positive pressure ventilation, ECMO, clinical diagnosis respiratory failure (i.e., clinical need for one of the preceding therapies, but preceding therapies not able to be administered in setting of resource limitation)
  - B. Hemodynamic compromise (defined by systolic blood pressure < 90 mm Hg, or diastolic blood pressure < 60 mm Hg or requiring vasopressors)
  - C. Multi-organ dysfunction/failure
7. Time to clinical improvement from baseline value (defined by time to  $\geq 1$ -point improvement on the WHO Ordinal Scale for COVID-19 score – must be maintained through Day 28)
8. Mean change from baseline in WHO Ordinal Scale for COVID-19 score at Day 14/EOT, Day 28, Day 57
9. Incidence and duration of intubation
10. Length of intensive care unit stay
11. Incidence and duration of supplemental O2 administration
12. Incidence and duration of noninvasive ventilation or high-flow nasal cannula O2 administration
13. Incidence and duration of mechanical ventilation
14. Incidence and duration of mechanical ventilation plus additional organ support using vasopressors, and/or renal replacement therapy and/or ECMO
15. Daily ratio of oxygen saturation (SpO2) to fractional inspired O2 (SpO2/FiO2)
16. Length of hospital stay
17. Incidence of re-hospitalization through Day 57
18. Proportion of subjects requiring intensive care unit admission post randomization

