10.2.1 Proportion of binary endpoints

The number and percentage of the following binary endpoints will be presented by treatment and timepoint. Comparison of proportion of patients between treatment at each timepoint will be analysed by the same manner as primary endpoint.

- Proportion of patients who had survived at each timepoint at Day 14, at Day 28, at Day 57: which is defined as patients who had no documented death prior or on timepoint at Day 14, 28, 57.
- Proportion of patients who survive without progression to RF at each timepoint at Day 14, Day 28, Day 57: which is defined as patients who had neither documented death nor respiratory failure prior or on timepoint at Day 14, 28, 57.
- Proportion of patients who had intubation during the study: which will be defined as proportion of patients who had any documented intubation during the study.
- Proportion of patients who develop critical COVID-19 illness as defined by at least one the following:
 - A. Respiratory failure defined based on resource utilization requiring at least one of the following: Endotracheal intubation and mechanical ventilation, oxygen delivered by high-flow nasal cannula (heated, humidified, oxygen delivered via reinforced nasal cannula at flow rates > 20 L/min with fraction of delivered oxygen ≥ 0.5), noninvasive positive pressure ventilation, ECMO clinical diagnosis respiratory failure (i.e., clinical need for one of the preceding therapies, but preceding therapies not able to be administered in setting of resource limitation)
 - B. Hemodynamic compromise (defined by systolic blood pressure < 90 mm Hg, or diastolic blood pressure < 60 mm Hg or requiring vasopressors)
 - C. Multi-organ dysfunction/failure
- Proportion of patients requiring intensive care unit admission: which is defined as patients who had been admitted to intensive care unit during the study.
- Incidence of supplemental O₂ administration: which will be defined as proportion of patients who had any documented post-dosing supplemental O₂ administration during the study.
- Incidence of noninvasive ventilation or high-flow nasal cannula O₂ administration: which will be defined as proportion of patients who had any documented post-dosing noninvasive ventilation or high-flow nasal cannula O₂ administration.
- Incidence of mechanical ventilation: which will be defined as proportion of patients who had any documented post-dosing mechanical ventilation.

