- Incidence of mechanical ventilation plus additional organ support using vasopressors, and/or renal replacement therapy and/or ECMO: which will be defined as proportion of patients who had any documented post-dosing mechanical ventilation plus additional organ support using vasopressors, and/or renal replacement therapy and/or ECMO.

QMS Document Name: Statistical Analysis Plan	Page 20 of 27
QMS No (include version ref): STF-015-GL.02	Document date: 09JUL2019
CONFIDENTIAL	

- Incidence of re-hospitalization through Day 57: which will be defined as proportion of patients who are hospitalized again after the discharge of first hospitalization.

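### In SAP 10.2.1 a death without the event counts as a non-event for re-hospitalization, intubation, ventilation, ICU admission and (less so) critical illness, so these comparisons can favour the arm with more deaths

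*SAP*

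**What the plan says.** SAP 10.2.1 defines these binary secondary endpoints by occurrence of the event only:

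- Intubation: "proportion of patients who had any documented intubation during the study".
- Mechanical ventilation: "proportion of patients who had any documented post-dosing mechanical ventilation". The version with added organ support has the same form.
- ICU admission: "which is defined as patients who had been admitted to intensive care unit during the study".
- Re-hospitalization through Day 57: "proportion of patients who are hospitalized again after the discharge of first hospitalization".
- Critical illness: "Proportion of patients who develop critical COVID-19 illness as defined by at least one the following", namely respiratory failure (A), hemodynamic compromise (B) or multi-organ dysfunction/failure (C). Within A, the route by clinical diagnosis is limited to "clinical need for one of the preceding therapies, but preceding therapies not able to be administered in setting of resource limitation" (also Protocol 2.3.2, no. 6).

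The default denominator is every patient in the analysis set and treatment group (SAP 4.1). Secondary efficacy endpoints are analysed in the ITT set on observed data, without imputation unless specified (SAP 10.2). The arms are compared by the same method as for the primary endpoint (SAP 10.2.1), with confidence intervals and uncorrected p-values (Protocol 8.4).

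The plan does deal with death elsewhere. The primary endpoint is "Proportion of subjects who have died or progressed to RF" (Protocol 2.3.1). SAP 10.2.1 itself lists survival and survival without RF at Days 14, 28 and 57. WHO scores carry early deaths forward to Day 28 (SAP 4.4), and the censoring rule for time to clinical improvement mentions death (SAP 10.2.2).

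**The concern.** For the listed endpoints no rule says what happens to a subject who dies without the event. Such a subject stays in the denominator and adds nothing to the numerator. The missing-data rule does not help, because the event status of a dead subject is not missing. Using the primary endpoint's comparison method does not change the endpoint definitions either.

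Re-hospitalization is the clearest case. Death before first discharge makes the event impossible, so early mortality lowers the rate directly. Critical illness is the weakest case, since many dying subjects would meet A, B or C first. It is still possible to miss them: vital signs are scheduled daily only to Day 14, Table 1 shows none at Day 57, and the Day 57 visit is a telephone call (Protocol 7.1.2.2). A late death at home could have none of A to C documented.

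At stake is the reading of several between-arm comparisons. A lower rate of re-hospitalization or ventilation could be taken as benefit when it partly reflects more deaths. Equally, a real mortality benefit could show up as a higher readmission rate.

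**Working it through.** **Plan's own figure.** The documents state no figure for these endpoints. The only related one is the sample size of 312 (31% vs 15%, two-sided 5%, 90% power). It reproduces: the two-proportion formula with continuity correction gives 156 per arm, and exact enumeration of Fisher's test at 156 per arm gives power 0.905. It concerns the primary endpoint, which includes death, so it neither supports nor weakens this point.

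**Set-up.** In one arm, let *d* be the proportion who die without the listed event and *e* the event proportion among the rest. Take *e* equal in both arms to isolate the effect of death. Neither quantity is in the documents, so every value below is an assumption.

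- As defined: rate = *e*(1 − *d*). Difference, asapiprant minus placebo = −*e*(*d*A − *d*P).
- Event or death: rate = *d* + *e*(1 − *d*). Difference = (1 − *e*)(*d*A − *d*P).

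With equal *e* strictly between 0 and 1, the two differences have opposite signs whenever the death proportions differ. Both are zero when they are equal.

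**Results (placebo vs asapiprant).**

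| Assumed *e* | *d* | As defined | Diff. (points) | Event or death | Diff. (points) |
|---|---|---|---|---|---|
| 10% (readmission) | 10% vs 4% | 9.0% vs 9.6% | +0.6 | 19.0% vs 13.6% | −5.4 |
| 20% | 5% vs 10% | 19.0% vs 18.0% | −1.0 | 24.0% vs 28.0% | +4.0 |
| 20% | 2% vs 5% | 19.6% vs 19.0% | −0.6 | 21.6% vs 24.0% | +2.4 |
| 15% | 5% vs 10% | 14.25% vs 13.5% | −0.75 | 19.25% vs 23.5% | +4.25 |
| 20% | 5% vs 5% | 19.0% vs 19.0% | 0 | 24.0% vs 24.0% | 0 |

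First row in full: placebo 0.90 × 0.10 = 9.0%, asapiprant 0.96 × 0.10 = 9.6%; with the index-stay deaths, 10 + 9.0 = 19.0% and 4 + 9.6 = 13.6%. This row counts index-stay deaths only. A Day 57 composite would also count later deaths without readmission.

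**Second view, at the planned 156 per arm.** Suppose 48 of 156 in each arm have the event or die (30.8%), so the event-or-death difference is 0. All 48 on placebo have the event, while *k* of the 48 on asapiprant die without it.

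| *k* | As defined, asapiprant | Diff. (points) | Fisher p |
|---|---|---|---|
| 4 | 44/156 = 28.2% | −2.6 | 0.71 |
| 8 | 40/156 = 25.6% | −5.1 | 0.38 |
| 12 | 36/156 = 23.1% | −7.7 | 0.16 |
| 16 | 32/156 = 20.5% | −10.3 | 0.051 |

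Large imbalances are needed before the as-defined comparison nears significance. The SAP Addendum says that enrollment stopped before the interim analysis, so the actual number per arm may differ from 156.

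**The case against.** The strongest reply is that nothing here is an error. Events over all randomized subjects, with deaths kept in the denominator, is (with complete follow-up) the cumulative incidence with death as a competing event. That is a legitimate quantity, and choosing a composite instead is a choice of estimand. The incidences are listed in the protocol, and the intubation endpoint was put in its present form at FDA request (Summary of Major Protocol Changes). The critical-illness definition mirrors inclusion criterion 7, and adding death would overlap with RF-free survival. Protocol 8.4 treats these analyses as descriptive, names none as key and corrects none for multiplicity. All of this stands. It argues against replacing the incidences and limits the weight of the point. It does not remove the possible reversal of direction when the arms are compared.

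Three stronger readings are tempting, and the documents do not support them:

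- A reader might infer that the plan's binary endpoints ignore death, or that excess mortality would be hidden. Survival and RF-free survival are in the same SAP section, death is in the primary endpoint, and death scores 8 on the WHO scale used for time to worsening.
- A reader might infer that the SAP treats these deaths as successes. It only records whether each event occurred; the favourable reading comes from interpreting a lower rate as benefit.
- A reader might expect the problem to be worst at age 75 and over, or where escalation of care is limited. The documents contain nothing on either.

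The size is also modest in places. In the readmission example, 9.0% vs 9.6% is about 14 vs 15 subjects at 156 per arm, and it would stand beside a survival comparison showing the deaths.

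**Conclusion.** The point holds as a gap in interpretation for secondary endpoints. It is clearest for re-hospitalization, applies to intubation, mechanical ventilation and ICU admission, and is probably smallest for critical illness. The primary conclusion does not depend on it. Under the assumed rates, the as-defined differences are at most 1.0 point, while event-or-death moves 2.4 to 5.4 points the other way. The constructed case with equal event-or-death shows how far the as-defined contrast could drift on its own. These sizes rest on assumed death and event rates, and bias between arms requires unequal deaths without the event. No passage supplies a rule that closes the gap, and the remedy discards no planned result, so it is worth making.

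**What to change.** Revise SAP 10.2.1 as follows:

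1. Keep the protocol-listed incidences and present them as component counts.
2. Add a treatment comparison of re-hospitalized or died by Day 57.
3. Add event-or-death comparisons for intubation, mechanical ventilation (with and without organ support), ICU admission and critical illness, each with a stated time frame.
4. For each endpoint, show by arm the number who died without the event. For re-hospitalization, also show deaths before first discharge.
5. State that any interpretation of treatment benefit rests on the event-or-death comparison.

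No new data are needed: deaths are already analysed at Days 14, 28 and 57 and summarized under SAP 11.2. SAP section 1 requires a protocol amendment for changes to the primary endpoint or analysis, which this is not.

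The costs are a few extra tables, and composites that share the same deaths and overlap with RF-free survival. Timing also matters. The Addendum records that all enrolled patients have passed Day 28 and that blinded outcomes were reviewed, so the revision must be made before unblinding and dated as such.

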### 4.2 Inclusion Criteria

The subject will be considered eligible for the study after meeting all of the criteria below.

1. Ability to voluntarily provide informed consent that is documented per local requirements
2. An understanding, ability, and willingness to fully comply with study procedures and restrictions
3. Hospitalized subjects with a confirmed SARS-CoV-2 infection
4. Laboratory (polymerase chain reaction [PCR]) confirmed infection with SARS-CoV-2
5. Age  $\geq$  50 years
6. COVID-19 illness of any duration, and O2 saturation measurements  $\leq$  94% over 5 minutes on room air (Note: low flow O2 is permitted, but room air O2 saturation must be  $\leq$  94%)
7. Not with evidence of critical COVID-19 illness as defined by at least one of the following:
  - a. RF defined by requiring at least one of the following:
    - Endotracheal intubation and mechanical ventilation
    - O2 delivered by high-flow nasal cannula at flow rates > 20 L/min with fraction of delivered O2  $\geq$  0.5)
    - Noninvasive positive pressure ventilation (NIPPV)
    - Extracorporeal membrane oxygenation (ECMO)
    - Clinical diagnosis of RF (i.e., clinical need for one of the preceding therapies, but preceding therapies are not able to be administered in setting of resource limitation)
  - b. Hemodynamic compromise (defined by systolic blood pressure < 90 mm Hg, or diastolic blood pressure < 60 mm Hg) or requiring vasopressors
  - c. Multi-organ dysfunction/failure
8. Female subjects of childbearing potential must have a negative pregnancy test at screening or pre-treatment on Day 1

**Note:** Female subjects of childbearing potential are defined as pre-menopausal, < 12 months of amenorrhea post-menopause, or no history of surgical sterilization (hysterectomy or oophorectomy) or tubal ligation.

9. Male and female subjects of childbearing potential must agree to use methods of contraception that are consistent with local regulations for those participating in clinical studies

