2.3 Study Endpoints and Evaluations

Primary Endpoint

- Proportion of patients who have died or progressed to RF as defined by progressing to the need for high-flow nasal cannula O₂ delivery, noninvasive positive pressure ventilation, invasive mechanical ventilation, or extracorporeal membrane oxygenation (ECMO) therapy by Day 28.

Secondary Endpoints

1. Safety as assessed by AEs as measured by the Common Terminology Criteria for Adverse Events (CTCAE) v 5.0
2. Proportion of patients surviving [Time Frame: at Day 14, at Day 28, at Day 57]
3. Proportion of subjects who survive without progression to RF [Time Frame: at Day 14, at Day 28, at Day 57]

QMS Document Name: Statistical Analysis Plan	Page 9 of 27
QMS No (include version ref): STF-015-GL.02	Document date: 09JUL2019
CONFIDENTIAL	

4. Time to two successive negative viral titers in nasopharyngeal swab
5. Time to clinical worsening from baseline value (defined by time to ≥ 1 -point worsening on WHO Ordinal Scale for COVID-19):

World Health Organization Ordinal Scale for COVID-19

Patient State	Description	Score
Uninfected	No clinical or virological evidence of infection	0
Ambulatory	No limitation of activities	1
	Limitation of activities	2
Hospitalized, Mild Disease	Hospitalized, no oxygen therapy	3
	Oxygen by mask or nasal prongs	4
Hospitalized, Severe Disease	Noninvasive ventilation or high-flow oxygen	5
	Intubation and mechanical ventilation	6
	Ventilation + additional organ support – pressors, RRT, ECMO	7
Dead	Death	8

Abbreviations: ECMO = extracorporeal membrane oxygenation; RRT = renal replacement therapy

6. Proportion of patients who develop critical COVID-19 illness as defined by at least one the following:
 - A. Respiratory failure defined based on resource utilization requiring at least one of the following: Endotracheal intubation and mechanical ventilation, oxygen delivered by high-flow nasal cannula (heated, humidified, oxygen delivered via reinforced nasal cannula at flow rates > 20 L/min with fraction of delivered oxygen ≥ 0.5), noninvasive positive pressure ventilation, ECMO clinical diagnosis respiratory failure (i.e., clinical need for one of the preceding therapies, but preceding therapies not able to be administered in setting of resource limitation)
 - B. Hemodynamic compromise (defined by systolic blood pressure < 90 mm Hg, or diastolic blood pressure < 60 mm Hg or requiring vasopressors)
 - C. Multi-organ dysfunction/failure

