4.3 Subgroups

The following sub-groups will be examined for the primary endpoint. Results will be displayed in both tabular form. Subgroup analyses are exploratory.

- Age (50 to < 75 vs \geq 75)
- Gender (male vs female)
- previous COVID-19 therapy (yes vs no)
- Regions (North America vs South America)
- Baseline WHO ordinal clinical scale (3 or 4)

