10.1 Primary efficacy analysis

The number and percentage of patients who have died or have progressed to RF through Day 28 will be presented by treatment. Hypothesis test comparison of proportion between treatment will be analyzed using a logistic regression with predefined covariates and treatment group. The predefined covariates are region and age group. Other covariates including previous COVID-19 therapy may be explored as exploratory analyses. Estimation of the covariate-adjusted risk difference will be reported using Cochran-Mantel-Haenszel (CMH) weighting and estimates from the logistic regression as described by Ge and colleagues (Ge et al., 2011, Appendix C). Two-sided p-value of global test comparison between active and placebo will be reported. Odds ratio of each covariate and two-sided 95% CI will also be reported. This analysis will be repeated without the covariates.

The denominator for the proportions alive and RF-free at Day 28 will include all randomized subjects.

Time from date of randomization to death or first RF through Day 28, whichever comes first, will also be displayed using the Kaplan-Meier estimator and analyzed using a proportional hazards model analysis with the same covariates. If a patient doesn't have documented death or RF, it will be censored at the Day 28. For subject who discontinued study before Day 28 without documented outcome, it will be censored at the date of discontinuation. This analysis will be repeated without the covariates. Test statistics will be the Hazard Ratio with 95% CIs and p-values. Sensitivity test will be done using a Fishers Exact Test.

Primary endpoint will be analyzed using ITT, mITT, PPS (if formed) analysis set under randomized treatment.

Primary endpoint analysis will be repeated for subgroups as specified [section 4.3](#).

Sensitivity analysis and handling of missing primary endpoint data

If $\leq 5\%$ of subjects lack sufficient data to confirm the primary endpoint, four sensitivity analyses will be performed on logistic regression: 1) treat any missing primary outcomes as successes; 2) replaces

QMS Document Name: Statistical Analysis Plan	Page 18 of 27
QMS No (include version ref): STF-015-GL.02	Document date: 09JUL2019
CONFIDENTIAL	

any missing primary outcomes as failures; 3) missing primary outcome imputed as success for drug and failure for controls; 4) missing primary outcome imputed as failure for drug and success for controls.

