- 2) based blinded data review, all those subjects who had baseline WHO scale=3 had no respiratory failure, and therefore leading quasi-complete separation on primary endpoint.

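### Incidence of supplemental oxygen counts use continuing from baseline as well as new use, so any difference in new oxygen starts is diluted by the share of subjects already on oxygen

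*SAP*

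**What the plan says.** - **Definition.** SAP 10.2.1 gives incidence of supplemental oxygen as an endpoint "which will be defined as proportion of patients who had any documented post-dosing supplemental" oxygen at any time in the study. It does not require the use to be new and does not set aside subjects already on oxygen.
- **Entry.** Protocol 4.2, criterion 6, requires a room-air saturation of 94% or less and adds "Note: low flow O 2 is permitted, but room air O 2 saturation must be" at or below that level.
- **Baseline states.** The WHO scale in SAP 2.3 gives score 3 as "Hospitalized, no oxygen therapy" and score 4 as "Oxygen by mask or nasal prongs". SAP 4.3 names these two scores as the baseline subgroups, but for the primary endpoint only.
- **Model.** Binary secondary endpoints "will be analysed by the same manner as primary endpoint" (SAP 10.2.1). For the primary endpoint, "The predefined covariates are region and age group" (SAP 10.1). The SAP addendum (Section 16) records that baseline WHO score was taken out of that model.
- **Analysis sets.** SAP 10.2 uses ITT, mITT and, if formed, the per-protocol set. None is restricted by baseline oxygen status.
- **Standing.** Protocol 8.4 calls these secondary analyses descriptive, names none as key, applies no multiplicity correction, and adds Fisher's exact test for incidence.

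**The concern.** A rate called incidence is normally read as new occurrence after treatment starts. Here a subject on nasal prongs at baseline who is still on them after the first dose is counted, whatever the treatment does. The proportion therefore has a floor close to the share of subjects on oxygen at entry, and only subjects off oxygen at baseline can show a difference in new starts.

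The same any-post-dose wording does no such harm for mechanical ventilation or noninvasive ventilation, because criterion 7 keeps out subjects already receiving them. Supplemental oxygen is the case where the treatment counted as an outcome is allowed at entry.

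At stake is interpretation. A small or absent difference could be reported as no effect on the need for oxygen when much of it reflects who was already on oxygen at randomization. Randomization is stratified by region and age, not oxygen status, so the design does not balance this share either.

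**Working it through.** **The plan's own figure.** The documents give no expected rate, sample size or power for this endpoint. The only stated figure is 312 in total for the primary endpoint (31% against 15%, Fisher's exact test, two-sided 5%, 90% power). The continuity-corrected two-proportion formula gives 156 per arm, 312 in total (144 per arm, 288 in total, without the correction). Exact Fisher power at 156 per arm is 90.5%. The planned size reproduces and is used below.

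**Inputs.**
- From the documents: 156 per arm and two-sided 5% (SAP 2.2); Fisher's exact test for incidence (Protocol 8.4); the event definition (SAP 10.2.1).
- Assumed, because the documents give neither: the share *f* on oxygen at baseline, taken as 50 to 90%, and the new-start rate *q* among the rest, taken as 60% on placebo and 30% on asapiprant.
- Also assumed: every subject on oxygen at baseline is still on it after the first dose.

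**Formula.** The rate as defined is p = f + (1 − f)q in each arm. The difference between arms is (1 − f) × (q placebo − q active), so a true 30-point difference is multiplied by (1 − f). For example, at f = 0.7 the rates are 0.7 + 0.3 × 0.6 = 0.88 and 0.7 + 0.3 × 0.3 = 0.79, a difference of 9 points.

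**Results, exact Fisher power by full enumeration.**

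| On oxygen at baseline | Rates as defined | Difference | Power, all subjects (156 per arm) | Off oxygen, per arm | Power, off-oxygen subset |
|---|---|---|---|---|---|
| 50% | 80% vs 65% | 15 points | 82% | 78 | 95% |
| 70% | 88% vs 79% | 9 points | 52% | 47 | 79% |
| 80% | 92% vs 86% | 6 points | 33% | 31 | 59% |
| 90% | 96% vs 93% | 3 points | 14% | 16 | 27% |

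**Other effect sizes.** With new starts of 50% against 25%, power as defined is 62, 34, 21 and 10% over the same four shares, against 88, 64, 44 and 18% in the subset. With 50% against 0%, power as defined is still 87% at a 70% share and 65% at an 80% share.

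**Smaller trial.** The addendum says that enrolment stopped before the interim analysis, which was planned at about 208 subjects. The final number is not given. With 104 per arm as an illustration (208 / 2) and 60% against 30%, power as defined is 63, 35, 22 and 9%.

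**Adding baseline score to the model.** If every score 4 subject is an event, that stratum says nothing about treatment. An analysis stratified by baseline score would then draw on the score 3 subjects alone, as the restricted definition does.

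**The case against.** **Other endpoints cover much of this ground.** Time to improvement of at least one point, for a score 4 subject, is largely time to coming off oxygen. Duration of supplemental oxygen is analysed with baseline WHO score in the model (SAP 10.2.4). Time to worsening, for a score 3 subject, captures a new need for oxygen or worse. This stands for score 4 subjects, and nothing new is needed for them. For score 3 subjects it stands only in part, because the worsening endpoint pools them with score 4 subjects moving to score 5.

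**The wording could mean episodes that begin after dosing.** The duration endpoint refers to a first post-dose episode with start and end dates. That reading is possible, but the incidence definition asks only for documented use after dosing. The ambiguity is itself a reason to fix the text.

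**Not every score 4 subject need be an event.** Baseline is the last assessment before randomization (SAP 4.7), so a subject weaned before the first dose would not count. This is correct, and it makes the assumption in the working an upper bound on automatic events.

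**A reader might infer that the endpoint sits near its ceiling and cannot show a treatment effect, or that a null result would say nothing about the drug.** The documents do not support this. The share at score 4 is not stated. A saturation of 94% or less at entry makes a high share plausible but does not establish it. Score 3 subjects were enrolled: the addendum reports that "all those subjects who had baseline WHO scale=3 had no respiratory failure". Power falls as the share rises but does not vanish, and at a 50% share it is 82% in the scenario above.

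**Conclusion.** The point holds as one of definition and dilution. As written, the endpoint reports continuing and new oxygen use together under the name of incidence, and the planned model does not adjust for baseline WHO score. Any difference in new starts is multiplied by one minus the share already on oxygen.

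In the main scenario, power as defined is lower than in the off-oxygen subset by 13 points at a 50% share (95 − 82), 27 at 70% (79 − 52), 26 at 80% (59 − 33) and 13 at 90% (27 − 14). These sizes rest on an assumed oxygen share, assumed new-start rates, the planned rather than the actual enrolment, and all score 4 subjects counting as events.

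The importance is low. This is one of many uncorrected, non-key secondary endpoints with companion measures. The primary analysis, the sample size and the safety analyses are unaffected.

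**What to change.** In SAP 10.2.1, define incidence of supplemental oxygen as new use after the first dose among subjects with baseline WHO score 3, and report the difference between arms with a 95% confidence interval. Keep the all-subjects proportion as a descriptive figure, shown separately for baseline scores 3 and 4, and state that it includes continuing use. For score 4 subjects, refer to the existing duration of supplemental oxygen and time-to-improvement endpoints.

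The cost is SAP wording and one table. Baseline score is already collected and defined, and oxygen start and end dates are already used for duration. If treatment codes have been opened by the time of the change, label the restricted analysis as post hoc.

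The downside is that the comparison rests on fewer subjects, possibly very few: about 16 per arm if 90% of the planned 156 were on oxygen at baseline. It should then be read as an estimate with its interval rather than as a test.
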